3.1 Scope of the Analysis

The first interim analysis was completed using data on or before 30 November 2010 to obtain preliminary results on the longer term safety and efficacy of adalimumab in pediatric Crohn's disease (CD), beyond the 52 weeks of the parent Study M06-806. The principal purpose of the first interim analysis was to evaluate the safety of the study drug. The efficacy variables, clinical remission and clinical response based on Pediatric Crohn's Disease Activity Index (PCDAI) and Crohn's Disease Activity Index (CDAI) were summarized over time. Information on demographic, baseline characteristics and prior/concomitant medications of the enrolled subjects were also provided.

The second interim analysis was performed using data on or before 31 July 2011. Similar variables on safety, efficacy, demographic, baseline characteristics and prior/concomitant

medications of the enrolled subjects were provided. In addition, the dose de-escalation population which consists of all subjects who have responded well to treatment and had dose and/or frequency decrease per protocol Amendment 4 were examined.

The third interim analysis was performed using data with an associated cutoff date of 31 January 2015. In addition to the analyses performed in the second interim analysis, corticosteroid-free remission and concomitant corticosteroid-free remission were added as new efficacy variables. Subgroup analysis was conducted on some safety and efficacy variables.

The final analysis will be performed using final data.

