4.2 Study Design

This study is a multicenter, open-label study of the human anti-TNF monoclonal antibody adalimumab. Thirty-one sites participated in Study M06-807. Approximately 130 pediatric subjects were expected to enroll in this study; final enrollment was 100 subjects.

Subjects were allowed to enroll in Study M06-807 if they participated in and successfully completed Protocol M06-806 through Week 52. A subject must have been a responder at any time point during Study M06-806. A responder was defined as a subject who had a PCDAI that was at least 15 points lower than the Study M06-806 baseline PCDAI.

All subjects were on open-label maintenance therapy during Study M06-807. Subjects who enrolled into the study from blinded therapy in Study M06-806 received open-label therapy at a dose dependent on their body weight. Subjects who weighed ≥ 40 kg at Baseline (the Week 52 visit of Study M06-806) received 40 mg eow of adalimumab, while subjects who weighed < 40 kg at Baseline received 20 mg eow of adalimumab. Beginning at Week 8, subjects who had a disease flare may have been switched to ew treatment at the same dose of adalimumab received while on eow treatment. A disease flare was defined as an increase in the Pediatric Crohn's Disease Activity Index (PCDAI) of ≥ 15 points when compared to the PCDAI obtained at the subject's previous visit.

Subjects who enrolled into the study from open-label therapy in Study M06-806 continued to receive the same dose they were receiving (i.e., 40 mg ew or 20 mg ew) at the Week 52 visit of Study M06-806.

Subjects who developed a flare while receiving ew open-label therapy or had a PCDAI ≥ 15 points when compared to their Baseline (the Week 52 visit of Study M06-806) PCDAI (regardless of study visit), may have been discontinued from the study at the discretion of the Investigator.

Beginning from Week 8, the dose of adalimumab may have been increased to 40 mg, at the discretion of the Investigator, for subjects whose body weight had increased from < 40 kg to ≥ 40 kg from Baseline (the Week 52 visit of Study M06-806). The site entered the subject's body weight into the Interactive Voice Response System (IVRS) and the dose would have been adjusted, if applicable.

Reductions in concomitant therapy were allowed for Crohn's treatment related toxicities (e.g., leukopenia, anemia, neuropathy) of Grade 3 or higher.

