Subjects may have been allowed to decrease prednisone (or equivalent) and budesonide if qualifications were met (Section 5.2.3.2 of protocol for required timing and rate of taper).

Subjects may have been allowed to adjust their Crohn's specific concomitant medications as specified in Section 5.2.3.2 of protocol.

The duration of the study could last up to 408 weeks (approximately 8 years). Subjects who completed, or who early terminated from the study were to be contacted 70 days after their last dose of study drug to obtain information on any ongoing and new adverse events.

This study was to be concluded approximately 12 weeks after the following criteria were satisfied:

- Study drug received country and local (if applicable) regulatory approval for pediatric Crohn's Disease.
- All applicable local reimbursement procedures were completed.

[figure not shown]
Sites were notified once these criteria were met.

Following country and local (if applicable) regulatory approval and applicable local reimbursement approval of the study drug in a country, subjects should have returned to their next scheduled study visit as specified in the protocol. The termination visit should have been conducted in place of their regular scheduled study visit. These subjects should have been considered as having completed the study.

[figure not shown]
After completion of Study M06-806 and consideration of efficacy, safety and population pharmacokinetic results in conjunction with exposure-response modeling and simulation, it was observed that both the Low-Dose and High-Dose treatment provided evidence of efficacy and safety. Therefore, in order to minimize the systemic exposures to study drug to the lowest doses necessary in children with CD, Amendment 4 provided investigators with the option of dose de-escalation by reducing the dose or switching from ew to eow based on the clinical status of the individual patient. In addition, since the 10 mg eow dose was efficacious in subjects weighing < 40 kg in Study M06-806 patients had the option to be switched to this dose based on their body weight and clinical status at the discretion of the investigator. Subjects who experienced a disease flare may have re-increased their dosage or dose frequency to the next higher treatment level regardless

of prior dose or dose frequency decrease. A schematic of the study design is shown in [Figure 1](#) (prior to Amendment 4) and in [Figure 2](#) (after Amendment 4).

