5.0 Analysis Populations

5.1 Definition of Analysis Populations

The following two study populations will be used for analyses in this study.

Intent-To-Treat (ITT) Population: The ITT population consists of all subjects who received at least one dose of adalimumab in Study M06-807 and also had at least one non-missing efficacy measurement during the study. The ITT population will be used for efficacy analyses in this study.

Safety Population: The safety population consists of all subjects who received at least one dose of adalimumab in Study M06-807. The safety population will be used for safety analyses in this study.

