10.2 Analysis of Adverse Events

Adverse events will be coded using version 19.1 of the Medical Dictionary for Regulatory Activities (MedDRA). Adverse event data will be summarized and presented using primary MedDRA system organ classes (SOCs) and preferred terms (PTs). The system organ classes will be presented in alphabetical order and the preferred terms will be presented in alphabetical order within each system organ class. The following two types of tables are planned:

1. Crude incidence rate, i.e., the number and percent of subjects with treatment-emergent AEs will be tabulated.
2. Events per 100 patient years of observation: The number of AEs per 100 patient-years of observation will be tabulated.

Treatment-emergent adverse events are defined as new events that begin either on or after the first dose of the study medication in Study M06-806 and within 70 days after the last dose of the study medication in Study M06-807. The treatment-emergent adverse events listed below are of special interest:

- Any adverse event (AE),
- Any serious AE,
- Any AE leading to discontinuation,
- Any severe event,
- Any at least possibly drug-related AE,
- Any at least possibly drug-related serious AE,
- Any AE leading to death,
- Any infection,
- Any serious infection,
- Any legionella infection,
- Any diverticulitis,
- Any opportunistic infection excluding oral candidiasis and TB,
- Any oral candidiasis,
- Any tuberculosis,
- Any active tuberculosis,
- Any latent tuberculosis,
- Any parasitic infection,
- Any reactivation of hepatitis,
- Any progressive multifocal leukoencephalopathy (PML),
- Any malignancy,
- Any lymphoma,
- Any hepatosplenic T-cell lymphoma (HSTCL),
- Any non-melanoma skin cancers (NMSC),
- Any melanoma,
- Any leukaemia,

- Any malignancy other than lymphoma, HSTCL, leukaemia, NMSC or melanoma,
- Any allergic reaction including angioedema/anaphylaxis,
- Any lupus-like reactions and systemic lupus erythematosus,
- Any vasculitis,
- Any cutaneous vasculitis,
- Any non-cutaneous vasculitis,
- Any sarcoidosis,
- Any autoimmune hepatitis,
- Any myocardial infarction,
- Any cerebrovascular accident,
- Any CHF,
- Any pulmonary embolism,
- Any interstitial lung disease,
- Any intestinal perforation,
- Any intestinal stricture,
- Any pancreatitis,
- Any Stevens-Johnson Syndrome,
- Any erythema multiforme,
- Any worsening/new onset of psoriasis,
- Any demyelinating disorder,
- Any amyotrophic lateral sclerosis,

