Treatment-emergent AEs (TEAEs) will be listed if less than five subjects had AE data in the dose de-escalation set. Otherwise, the number and percentage of subjects with TEAEs and TEAEs per 100 patient-years will be summarized for the dose de-escalation set. The collection periods for the dose de-escalation set are defined as any event with onset on or after the first dose of ADA treatment in Study M06-806 and up to 70 days after the last study drug injection.

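### The only AE summary for the dose de-escalation set runs from the first M06-806 dose, so it mixes time before and after the decrease, and no planned summary gives AE incidence or rate after it

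*SAP*

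**What the plan says.** At its end, SAP Section 10.2 plans an AE output for the dose de-escalation set. If fewer than five subjects in the set have AE data, the events are listed. Otherwise the plan is the count and share of subjects with a treatment-emergent AE, and the event rate per 100 patient-years. The collection period covers "any event with onset on or after the first dose of ADA treatment in Study M06-806" and closes 70 days after the last injection. This is the same start as the general definition earlier in the section, which counts "new events that begin either on or after the first dose of the study medication in Study M06-806".

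The set is described in Section 3.1, under the second interim analysis, as "all subjects who have responded well to treatment and had dose and/or frequency decrease per protocol Amendment 4". Section 5.1 does not mention it. That section says "The following two study populations will be used for analyses in this study" and then names only the ITT and Safety populations.

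Section 4.2 fixes the order of events. Subjects could enter M06-807 "if they participated in and successfully completed Protocol M06-806 through Week 52". The decrease option arrived later: "After completion of Study M06-806 and consideration of efficacy, safety and population pharmacokinetic results", the text explains, "Amendment 4 provided investigators with the option of dose de-escalation". The same section allows a subject who flares to go back up to the next treatment level, whatever decrease came before.

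**The concern.** The set is defined by an event during follow-up, but its AE window is not tied to that event. What results is the overall AE table restricted to subjects who at some later point had a decrease. Section 4.2 gives lower systemic exposure as the reason for the decrease, so a reader will naturally look to this table for AE experience on the reduced regimen. It cannot supply that, because AEs and patient-years from the earlier regimen, and from any time after a re-increase, are in the same totals.

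The listing threshold has the same weakness. It is judged over the whole window, so AEs before the decrease can trigger a summary table even if few or none came after it.

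**Working it through.** The SAP states no figure on this point, so there is nothing to reproduce. The check has two parts.

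**1. Does any other planned output give AE incidence or rate after the decrease?**

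- Section 8.0: counts the subjects who de-escalated. No AE data.
- Section 10.2, general tables: all treated subjects over the whole treatment-emergent period. No split at a dose change.
- Section 10.2, listings: single events can be placed in time, but no patient-years and no denominator are given.
- Section 10.5: serious infections by immunomodulator and corticosteroid use, not by dose change.
- Section 6.0, partial AE dates: an AE with a partial start date in the month a new therapy began is assigned to that therapy. This is a date-imputation rule, not a summary.

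None does.

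**2. How much of the window must precede the decrease?**

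Inputs:

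- M06-806 time per member: 52 weeks (Section 4.2), assuming the first adalimumab dose was at the start of those 52 weeks.
- Longest M06-807 duration: 408 weeks (Section 4.2).
- Tail after the last injection: 70 days = 10 weeks (Section 10.2).
- Patient-years are assumed to follow the event window; the text on the set does not say so.

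With T the M06-807 week of the decrease and L the M06-807 week of the last injection:

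pre-decrease share = (52 + T) / (52 + L + 10)

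The share is smallest for a decrease on M06-807 Day 1 and the longest possible follow-up (T = 0, L = 408):

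52 / (52 + 408 + 10) = 52 / 470 = 0.111, about 11%.

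A later decrease or a shorter follow-up raises it. Neither T nor L is given for any subject, so the documents support nothing beyond this lower bound.

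**What pooling does to the rate.** The pooled rate is a weighted average. With pre-decrease share s and a post-to-pre rate ratio R, pooled rate / pre-decrease rate = s + (1 − s)R. At the lower bound, a hypothetical R = 2 gives 0.111 + 0.889 × 2 = 1.89, and R = 0.5 gives 0.111 + 0.889 × 0.5 = 0.56. At the bound the distortion is modest. It grows with s, and a reader of the table cannot tell how far. Time after a re-increase mixes the total further.

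**Does the other treatment-emergent start remove the problem?** Section 6.0, below Table 4, opens the treatment-emergent window at the first M06-807 injection, in conflict with Section 10.2. That start would drop the 52 parent-study weeks. It would still include all M06-807 time before the decrease for anyone who decreased after the first M06-807 injection, so pooling remains.

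**The case against.** The strongest reply is that this is an extra analysis rather than a mistake. Section 10.2 states its window, and nothing in the SAP presents the table as post-decrease experience. The objective in Section 4.1 concerns repeated administration over the long term and does not single out the reduced regimen. Using the general treatment-emergent start keeps the set on the same basis as the Safety population, and safety is descriptive with no tests. All of this stands, and it limits the point to an improvement in one table. It does not answer the observation that a set formed by dose decrease gets no AE summary tied to the decrease.

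The set may also be small. The study enrolled 100 subjects, and the plan itself provides for fewer than five in the set having AE data. Missing dosing dates are not imputed (Section 6.0), so the first reduced injection may be hard to place for some subjects. This stands too, and argues for one added summary rather than an elaborate layout by period.

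Three stronger readings are tempting and are not supported:

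- *Most of the window precedes the decrease.* A reader might infer this from the length of the programme. The SAP gives no decrease dates. The set was already examined with data to 31 July 2011 (Section 3.1), and the final analysis comes after a protocol amendment of 26 May 2015 (Section 3.0), so some members may have long follow-up after the decrease.
- *Rates of AEs that end participation are diluted by a known factor.* Members had to be still on study in order to decrease, so a reader might infer this. But "Any AE leading to discontinuation" stands in the general list, and no output of that kind is assigned to this set.
- *The set is undefined.* Section 3.1 describes it, so its absence from Section 5.1 is mostly editorial.

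**Conclusion.** The point holds in limited form. The table for the dose de-escalation set describes all adalimumab exposure in subjects who ever de-escalated, and cannot be read as AE experience after de-escalation. No other planned summary fills that gap. At least 52 weeks per member, about 11% or more of the window, precede the decrease. This assumes that adalimumab began at the start of those 52 weeks and that patient-years follow the event window. Beyond that lower bound the size is unknown.

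The consequence is confined to interpretation of one descriptive table. The overall safety tables, the efficacy summaries and the study's conclusions on long-term safety do not depend on it. The conflict between Sections 6.0 and 10.2 on the treatment-emergent start is a separate contradiction and adds no weight here.

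**What to change.** - Keep the pooled summary, but title it as all adalimumab exposure in subjects who ever de-escalated.
- Add one summary for the same set: treatment-emergent AEs with onset from the first injection under the reduced dose or frequency to the earlier of (a) the first later increase in dose or frequency and (b) the last injection plus 70 days. Cut patient-years at the same dates, and base n (%) on subjects who entered that period.
- Apply the fewer-than-five listing rule to that period rather than to the whole window.
- Do not present the added summary beside the pooled or earlier data as a before/after comparison, since membership depends on later response.
- State in Section 5.1 that the set described in Section 3.1 applies to the final analysis.
- Separately, reconcile the treatment-emergent start in Section 6.0 (first M06-807 injection) with Section 10.2 (first M06-806 dose).

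The cost is a few lines of SAP text and one more descriptive table programmed from recorded dosing dates. No new data are needed. The downside is that the post-decrease period may hold few events and patient-years, and may end up as a listing only.

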10.3 Analysis of Laboratory Data

A summary of all analyses (shift tables and change from Baseline) for clinical laboratory parameters is presented in [Table 5](#). A listing of all subjects with any clinical laboratory determinations meeting Common Toxicity Criteria (CTC) Version 3.0 of Grade ≥ 3 will be provided.

Table 5. Summary of Clinical Laboratory Analyses

Parameter	Clinical Laboratory Analysis
Hematology Results	Mean change from Baseline to minimum, maximum, and final Shift table from Baseline to worst CTC toxicity grade Identify subjects with CTC toxicity grade 3 or worse
Clinical Chemistry Results	Mean change from Baseline to minimum, maximum, and final Shift table from Baseline to worst CTC toxicity grade Identify subjects with CTC toxicity grade 3 or worse
Urinalysis Results	Mean change from Baseline to minimum, maximum

Changes from baseline in continuous laboratory parameters will be summarized over all treated subjects by n, mean, standard deviation and median values.

Cross (Shift) tables from baseline to the final value (i.e., the last non-missing value available) according to the normal range will be provided for each hematology, clinical chemistry parameter and urinalysis parameters.

For selected laboratory parameters with CTC grades, a listing of all subjects with any laboratory determinations meeting Grade > 3 will be provided. For each of these subjects, the whole course of the parameter will be listed. For subjects with laboratory values with Grade > 3, all of the laboratory parameters for those subjects will be listed.

The liver specific laboratory tests include the serum glutamic-pyruvic transaminase (ALT/SGPT), serum glutamic-oxaloacetic transaminase (AST/SGOT), alkaline phosphatase, and total bilirubin. Each of these laboratory values will be categorized as follows (ULN is the upper normal limit):

1. $< 1.5 \times \text{ULN}$,
2. $\geq 1.5 \times \text{ULN TO } < 3 \times \text{ULN}$,
3. $\geq 3 \times \text{ULN TO } < 5 \times \text{ULN}$,
4. $\geq 5 \times \text{ULN TO } < 8 \times \text{ULN}$, and
5. $\geq 8 \times \text{ULN}$.

Shift tables showing shift will be presented using the 5 categories listed above.

For liver specific laboratory tests, a listing of all observations collected will be generated for subjects that had at least one post-baseline observation meeting the pre-defined criteria for a potentially clinically significant (PCS) value. The number and percentage of subjects in each treatment group who have at least one post-baseline observation meeting the pre-defined criteria for PCS values will be provided for each variable.

Pre-defined criteria for PCS laboratory values are given in [Table 6](#) below:

Table 6. Potentially Clinically Significant Criteria for Laboratory Values

Chemistry Variables	Units	Definition of Potentially Clinically Significant	
		Very Low	Very High
Total Bilirubin	mcmol/L		> 1.5 × ULN
Serum glutamic-oxaloacetic transaminase (SGOT/AST) (Aspartate transaminase)	U/L		> 2.5 × ULN
Serum glutamic-pyruvic transaminase (SGPT/ALT) (Alanine aminotransferase)	U/L		> 2.5 × ULN
Alkaline phosphatase	U/L		> 2.5 × ULN

10.4 Analysis of Vital Signs and Weight

The following vital sign parameters will be obtained at each visit and summarized:

- Sitting systolic blood pressure [mmHg],
- Sitting diastolic blood pressure [mmHg],
- Pulse [bpm],
- Weight [kg],
- Height [cm],
- Respiratory rate [breaths per minute],
- Body temperature [°C].

Vital sign will be summarized following a similar procedure as described above for laboratory values. For continuous vital sign parameters, mean change from Baseline to minimum (smallest) value, maximum (largest) value, and final value will be summarized. Subjects with potentially clinically significant results will be identified according to the criteria in [Table 7](#), and shift tables will be provided.

Table 7. Criteria for Potentially Clinically Significant Vital Sign Results

Vital Sign	Criterion	Definition of Potentially Clinically Significant
Systolic blood pressure	Low	Value \leq 70 mmHg and decreased \geq 20 mmHg from initial value
	High	Value \geq 160 mmHg and increased \geq 20 mmHg from initial value
Diastolic blood pressure	Low	Value \leq 50 mmHg and decreased \geq 15 mmHg from initial value
	High	Value \geq 105 mmHg and increased \geq 15 mmHg from initial value
Pulse	Low	Value \leq 50 bpm and decreased \geq 30 bpm from initial value
	High	Value \geq 120 bpm and increased \geq 30 bpm from initial value

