4.3 Sample Size

Subjects who successfully completed Study M06-806 through Week 52 were eligible to participate in this study. One hundred (100) subjects from Study M06-806 were enrolled in this study.

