6.0 Analysis Conventions

Definition of Baseline

For the analysis of change and percent change, the baseline value for a variable is defined as the last non-missing value on or before the date of the first dose of study medication during the parent Study M06-806. Clinical response and remission based on CDAI and PCDAI will also be calculated using the Study M06-806 baseline values. The baseline values of the Study M06-806 will be reported for the subjects enrolled in the Study M06-807.

However, as mentioned in the next section, the visit windows used for the analysis are defined with respect to the first dose date during the Study M06-807.

Definition of Rx Days (Days Relative to the First Dose During Study M06-807)

Rx days are calculated for each time point relative to assigned visit. They are defined as the number of days between the day of the first dose of study drug in Study M06-807 and the specific time point. Rx days are negative values when the time point of interest is prior to the first study drug dose day. Rx days are positive values when the time point of interest is after the first study drug dose day. The day of the first dose of study drug in Study M06-807 is defined as Rx Day 1, while the day prior to the first study drug dose is defined as Rx Day -1 (there is no Rx Day 0).

Definition of Analysis Windows

All time points and corresponding time windows are defined based on Rx days. If more than one assessment is included in a time window the assessment closest to the nominal day should be used. If there were more than one observation with equal distance to the nominal day the latest one will be used in the analyses. For efficacy related analyses, if multiple measurements for a particular parameter are collected on the same day for the same subject, the average of those measurements will be used. For safety related analyses, if multiple measurements are made for a particular laboratory or vital sign parameter on the same day for the same subject, the average of the values will be used in

the analyses. For summaries and listings of shift from baseline and potentially clinically significant values all values will be considered in the analyses.

Table 2. Time Window for Measurements Done at Each Office Visit

Assigned Visit	Nominal Day	Time Window (Rx Day Range)
Week 0	1	≤ 1
Week 4	29	2 – 43
Week 8	57	44 – 71
Week 12	85	72 – 127
Week 24	169	128 – 211
Week 36	253	212 – 295
Week 48	337	296 – 379
Week 60	421	380 – 463
Week 72	505	464 – 547

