11.2 Efficacy Analysis

For subjects with corticosteroid use at Study M06-806 Baseline, the number and percent of them with corticosteroid-free remission and concomitant corticosteroid-free remission (per PCDAI and CDAI, as defined in Section 4.5) over time will be summarized.

Change from Baseline in total IMPACT III over time for patients at least 10 years old at Baseline, change from Baseline in WPAI scores over time, change from Baseline in "z" scores for height over time and change from Baseline in BMI over time will be summarized.

In addition, change from Baseline in hsCRP levels over time will be summarized. Due to a technical issue a number of blood samples were affected by an under-recovery of hsCRP. All hsCRP values will be kept in the database as initially reported and will be analyzed as such in the primary analysis. Additional sensitivity analyses will be performed to account for hsCRP values of affected samples as follows:

- all affected values will be considered as missing values in an observed case analysis.
- all affected values will be imputed using LOCF rule.

For Health Care Resource Utilization (HCRU), cumulative HCRU including number of physician visits; number of emergency room visits; number of hospital admissions; total number of days in hospital will be summarized for the ITT population. And the ratio of the total number of utilizations and the total time under observation will be calculated across all subjects. HCRU will be analyzed as observed only.

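### Table 7 uses one fixed set of blood pressure limits for all ages in a pediatric study, so its high blood pressure flags have little sensitivity in younger, smaller subjects

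*SAP*

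**What the plan says.** SAP Section 10.4 states: "Subjects with potentially clinically significant results will be identified according to the criteria in" Table 7. The blood pressure rows relevant here are:

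- High systolic: "Value \geq 160 mmHg and increased \geq 20 mmHg from initial value".
- High diastolic: "Value \geq 105 mmHg and increased \geq 15 mmHg from initial value".
- Low diastolic: "Value \leq 50 mmHg and decreased \geq 15 mmHg from initial value".

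Each row joins a level and a change, and both must be met. No row has an age, sex or height term.

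Other parts of the SAP bear on how the table works:

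- **Population.** Section 4.3: "One hundred (100) subjects from Study M06-806 were enrolled in this study". Sections 7.1 and 11.4 use categories below 13 years and below 40 kg, and Table 1 limits one questionnaire to subjects aged 10 or older.
- **Follow-up.** Section 4.2 allows up to 408 weeks. Table 2 lists 24 office visits after Week 0, and Table 1 takes blood pressure at each visit.
- **Which readings count.** Section 6.0 uses all values for potentially clinically significant (PCS) summaries, not one per window.
- **Reference value.** Section 6.0 defines baseline for change analyses as "the last non-missing value on or before the date of the first dose of study medication during the parent Study M06-806". Table 7 uses another term, *initial value*, which the SAP does not define.
- **Standardisation elsewhere.** Section 11.2 summarises "change from Baseline in 'z' scores for height over time". Blood pressure has no such treatment.
- **Standing of the output.** Section 10.1 lists vital signs among the primary safety parameters and plans descriptive summaries only.

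**The concern.** Resting blood pressure rises with age and body size. A fixed ceiling therefore sits much further above a small child's usual level than above a large adolescent's, and the same rise is flagged in one and not in the other. A near-zero high blood pressure count in the younger subjects would look reassuring, although the criterion could hardly have produced anything else. Corticosteroids may be restarted or increased during the study (Section 7.3), so a blood pressure rise is a relevant thing to look for.

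At the other end, a small child's usual diastolic pressure lies nearer the 50 mmHg floor, so repeated readings over years could produce some chance flags. The undefined *initial value* adds a second problem: two programmers could measure the change from different visits and produce different tables.

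**Working it through.** The SAP gives no flag rate, blood pressure distribution or lower age limit, so there is no planned figure to reproduce. Limits and visit count come from Tables 7 and 2. **All means, SDs and drifts below are assumptions.** Readings are taken as normal, and each criterion needs both its level and its change.

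**1. Rise needed before a high flag is possible (no SD assumed).** The rise needed is the larger of the change limit and the level minus the starting value.

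| Criterion | Start (mmHg) | Rise needed (mmHg) |
|---|---|---|
| Systolic | 100 | 160 − 100 = 60 |
| Systolic | 105 | 160 − 105 = 55 |
| Systolic | 120 | 160 − 120 = 40 |
| Diastolic | 58 | 105 − 58 = 47 |
| Diastolic | 62 | 105 − 62 = 43 |
| Diastolic | 72 | 105 − 72 = 33 |

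The 20 mmHg systolic change limit decides the outcome only for starting values of 140 or above.

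**2. High systolic, sustained true rise of 40 mmHg.** With between- and within-subject SDs 8 and 6, the SD of a reading is √(8² + 6²) = 10. The level is met with probability 1 − Φ((160 − mean − 40)/10). The observed rise has mean 40 and SD √(2 × 6²) = 8.5, so it reaches 20 with probability 1 − Φ(−2.36) = 99%. The change limit hardly matters. Simulation of 200,000 subjects per case with both limits applied gives the per-visit figures below to within 0.2 points, and also the per-subject figures.

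| Mean (mmHg) | z | Flagged per visit | Flagged at least once in 24 visits |
|---|---|---|---|
| 100 | 2.0 | 2.3% | 17% |
| 105 | 1.5 | 6.7% | 35% |
| 120 | 0.0 | 50% | 91% |

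For a sustained rise of 30 mmHg, the at-least-once figures are 1.7%, 6% and 58%. Put another way, with within-subject SD 8, a child whose true systolic is 130 reaches 160 at 1 − Φ(30/8) = 0.01% of visits, and at a true 140 at 1 − Φ(20/8) = 0.6%.

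**3. High diastolic, sustained true rise of 30 mmHg.** With SDs 5 and 6, the SD of a reading is √(5² + 6²) = 7.81. The level is met with probability 1 − Φ((105 − mean − 30)/7.81):

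- mean 58: z = 2.18, 1.5% of visits
- mean 62: z = 1.66, 4.8% of visits
- mean 72: z = 0.38, 35% of visits

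**4. Low diastolic, no true change (SDs 5 and 6).**

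- Level alone, Φ((50 − mean)/7.81): 15.3% of readings at mean 58 and 6.2% at mean 62.
- Level and a fall of at least 15 (bivariate normal; change SD √72 = 8.5, covariance with the reading 36): 2.2% and 1.3% of readings.
- At least one flag over 24 visits, no drift: 25% and 18% of children. At mean 72–76 the figures are 2.3% and 0.6%.
- With growth drift of 0.8 mmHg a year, counted from a parent-study baseline 52 weeks before M06-807: 13% and 8% with visits at the Table 2 weeks, and about 10% and 6% with 24 evenly spaced visits.

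That gives about 6–25% per child and about 2% of readings or fewer. With wider inputs (means 58–66, SDs up to 7 and 9), the ranges are 4–54% per child over 24 visits and 0.4–7.3% per reading.

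**5. Age of the reference value.** If *initial value* means the Section 6.0 baseline, it can be 52 + 408 = 460 weeks old, or 8.8 years. If it means the first M06-807 value, it is 52 weeks more recent and follows a year in the parent study.

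**The case against.** Table 7 is one descriptive output with no test attached. Section 10.4 also plans mean change to minimum, maximum and final value, and shift tables, and blood pressure disorders reported as adverse events are tabulated separately. The probabilities rest on assumed distributions, because the SAP gives neither an age mix nor observed values. All of this stands, and it limits the weight of the point. It does not remove it: pooled mean changes do not identify individual children, and the rises in step 1 follow from the limits and the starting value alone.

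A reader might go further in four ways that the documents do not support:

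- **That ordinary low diastolic values are flagged often.** Table 7 also requires a fall of at least 15 mmHg, which removes most readings at or below 50. The upper 25% per child needs all 24 visits with no growth in blood pressure, whereas Section 4.2 gives 408 weeks only as a maximum.
- **That growth alone produces high flags.** Growth can meet the change limit, but the level must still be reached. Rising pressure against an old baseline also makes a 15 mmHg fall less likely, so it reduces chance low-diastolic flags.
- **That the blood pressure rows cannot be interpreted.** The other planned summaries give context, and the high criteria work reasonably for subjects with higher usual pressures.
- **That pulse is affected too.** The limits are fixed there as well (for example "Value \geq 120 bpm and increased \geq 30 bpm from initial value"), but high-pulse flags came to at most 0.4% of readings under the assumed ranges, and no consequence was shown.

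It can also be said that Section 6.0 already settles the reference value. That is the natural reading, but Section 10.4 uses both terms, so a wording correction is still needed.

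**Conclusion.** The point holds for high blood pressure. Under the stated assumptions, a large sustained systolic rise is flagged at about 2–7% of visits in subjects with usual values of 100–105 mmHg, against half of visits at 120. The diastolic criterion shows the same pattern. The direction follows from the fixed limits; the percentages depend on the assumed means and SDs.

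For low diastolic, only a modest statement is supported: chance flags may accumulate in some unchanged children over long follow-up, and the required fall keeps them rare per reading. No claim is made about pulse. No efficacy result or statistical test is affected. The change is worth making because vital signs are a primary safety parameter and the sensitivity of this output depends on age.

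**What to change.** 1. Keep Table 7 unchanged, so that PCS counts remain comparable with the interim reports.
2. For visits before age 18, add a supplementary high/low blood pressure flag and a shift table standardised for age, sex and height. The SAP should name the pediatric reference and state the cut-offs so that the flag can be programmed.
3. In Table 7, replace *initial value* with the baseline defined in Section 6.0.

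The cost is SAP wording, one more descriptive table and a reference table in the program. Age, sex, height and blood pressure are already collected.

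Standardising does not remove chance flags from repeated visits. As an illustration, take cut-offs at the 1st and 99th percentiles of single readings, SDs 5 and 6, 24 visits and no change condition. About 13% of unchanged children would then be flagged low at least once, and 27% low or high. The new table should therefore also report flags per reading.
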